5.4.6.4 Treatment Compliance – Primary Source Data

Subjects will be instructed by study personnel on the importance of being compliant with the use of the study drug and non-study products.

CCI

(Section 5.1.2 – Schedule of Assessments). The subject-reported data in the dosing calendar will be used as the primary source data for calculating treatment compliance, per each CCL Results are uploaded to a secure portal for remote monitoring, with subject counseling, as needed, throughout the study.

Subjects will be instructed to return the study electronic tablet and all study medication at each study visit. Site personnel will review dosing compliance data since the last visit, derive treatment compliance for each **CC** and counsel/re-train subjects, if needed. Treatment compliance will be derived from the total expected doses and number of actual doses recorded, over a given visit interval.

Any missed dose will be considered a protocol deviation, based on recordings in the dosing calendar. Subjects should be appropriately counseled on the importance of following study drug dosing instructions and daily recordings in the dosing calendar.

Subjects should be reminded and encouraged to follow guidelines for non-study product use, throughout the study (Section 5.4.2 – Instructions for Use).

5.4.6.5 Treatment Compliance – Supportive Video Evidence

The assigned electronic tablet will also be used by subjects to capture videos of study drug application, for each \bigcirc , on a daily basis (Section 5.4.3 – Study Drug Application with Video Collection). The study drug label will be apparent in the video to confirm which product was applied to each side of the face (e.g., red label = right side of face, etc). All videos are collected and stored locally and securely on the electronic tablet. There are no video uploads or transfer from the local device. Only designated site staff will have access to view these videos on the electronic tablet.

Even though no videos will be uploaded to a central portal for remote viewing, the electronic dosing calendar will include a question whether the subject is collecting daily videos, which site staff can reference for remote monitoring and counseling.

While the dosing calendar data will be the primary source for reporting treatment compliance, daily videos are used for site staff to spot-check for proper use of study medication, and appropriately counsel and re-train subjects on the importance of following proper study drug instructions.

GALDERMA S.A. RD.06.SPR.202395 Amended Protocol 01/Global 9Jul2021 Page 47 of 101

At each visit, the subject will return the electronic tablet. Site staff will review videos and provide subject counseling and reminders on the importance of following study drug dosing instructions, throughout the study. At least two videos since the prior visit should be reviewed. Subjects who display repeated non-compliance based on video evidence, despite repeated counseling and re-training, should be discontinued from the study, based on investigator discretion.

Note: Subjects will be informed that videos will be reviewed to ensure proper use of study drug throughout the study; however, they will not be told how many videos will be reviewed. This non-disclosure allows subjects to be appropriately informed with sufficient detail of what study procedures will be performed and does not create any added risks to the subjects by withholding this level of detail. Preserving the notion that someone is watching is considered critical to maintaining the integrity of the split-face study design, as it provides motivation to remain compliant, while attempting to balance the administrative burden of daily video review by site staff, over a total treatment period of approximately 170 days, for each subject. The subject-reported dosing compliance data recorded on the electronic dosing calendar will be used to derive compliance, which is a common procedure used in clinical studies to reliably assess daily product use. Repeated noncompliance observed by video evidence should result in subject termination, based on investigator discretion.

At the end of the study, the electronic tablet will be collected, and all collected information fully removed by the clinical site and confirmed by the equipment vendor.

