Sponsor Request:	An indication that the study subject was removed from the study
	at the sponsor's request.
Other ^a :	This category is to be used for a subject who discontinues due to a
	reason other than as specified in the predefined categories above.
	Explain the reason for discontinuation in the comment section of
	the Exit Form.

^a If reason for discontinuation is "withdrawal by subject", "withdrawal by parent/guardian", "physician decision" or "other", the subject will be questioned to rule out the possibility of an AE (this should be documented in the comment section of the Exit Form).

^b Investigator may withdraw a subject for dramatic, clinically significant differences in appearance between the right and left sides of the face where full face treatment may be indicated, based on the investigator's clinical judgment.

The reason(s) for withdrawal will be documented in the CRF. Subjects who have been randomized will not be replaced by another subject.

Subjects who prematurely discontinue study drug will be encouraged to complete the scheduled study visits for safety purposes and for collecting at least the data for the primary endpoint, before study exit.

When a subject discontinues the study, he/she will be fully assessed whenever possible, and followed according to guidelines presented in Section 5.5.1 - Early Termination Visit.

Reasonable efforts will be made to contact subjects who are lost to follow-up (e.g., non-response/contact after 2 phone calls and a certified letter with return receipt). These efforts must be documented in the subject's file.

The Sponsor has the right to terminate the study at any time in case of SAEs or if special circumstances concerning the investigational product or the company itself occur, making further treatment of subjects impossible. In this event, the investigator(s) will be informed of the reason for study termination.

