5.4.10 Unblinding During the Clinical Study

At the initiation of the study, site staff will be instructed on the method to follow for emergency breaking of the blind. The randomization information for any particular subject may be made available to the investigator in the event of a medical emergency or an AE that necessitates identification of the study drugs for the welfare of that participant. Whenever possible, the investigator should consult with the medical monitor and the Sponsor before breaking the blind, to discuss the decision. Emergency un-blinding during the clinical study may be required for regulatory reasons (for expedited safety reporting).

GALDERMA S.A. RD.06.SPR.202395 Amended Protocol 01/Global 9Jul2021 Page 49 of 101

When the blinding code is broken, the reason must be fully documented. If the code is broken by the investigator, the subject must be withdrawn from the study after completing early termination procedures.

Advanced Clinical Pharmacovigilance should be contacted to report any unblinding (refer to Section 6.11.2.2.2 for Advanced Clinical Pharmacovigilance contact information). To avoid bias and to ensure the integrity of the blind, personnel directly involved with the ongoing conduct of the study from the Sponsor, CRO, or other investigational study centers will not have access to any information that may lead to unblinding.

The randomization code will remain blinded to all study sites and study team members until completion of the study, and after the study database has been locked.

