7.2 Sample Size Determination

The sample size calculation is based on the results of the study RD.06.SPR.118295 "A Multi-Center Study to evaluate Subject Reported Outcomes with use of trifarotene 50 μ g/g cream in the treatment of moderate facial and truncal acne vulgaris" and of the study RD.03.SPR.105061 "Effect of Adapalene 0.3% - Benzoyl Peroxide 2.5% gel versus vehicle gel on the risk of formation of atrophic acne scars in moderate to severe acne subjects".

In study RD.06.SPR. CCluster, the following results were obtained for the absolute change from baseline in total atrophic acne scar count at week 24:

Study	μTrifarotene	σTrifarotene
RD.06.SPR.CCI	-3.4	9.48

These results refer to a whole face treatment whilst in the current study a CCL the design is used. Moreover, due to the CCL the design is it is not possible to estimate the mean value and the variability of the difference in mean absolute change from baseline in total atrophic acne scar between treatment arms.

t there are no data for estimating the variability of the difference between trifarotene 50 μ g/g cream and vehicle cream.

In study RD.03.SPR.^{CCI} design was used and the following results were obtained for the absolute change from baseline in total atrophic acne scar count at week 24:

Study	µABPO Forte	σ ABPO Forte	μVehicle	σVehicle	μDiff	σDiff
RD.03.SPR.CCI						

Under the following hypotheses:

- Mean absolute change from baseline in total atrophic acne scar count at week 24 for trifarotene 50 μg/g cream is -1.7
- Mean absolute change from baseline in total atrophic acne scar count at week 24 for Vehicle cream is zero
- Difference absolute change from baseline in total atrophic acne scar count at week 24 between trifarotene 50 µg/g cream and vehicle cream is -1.7
- Variability of the difference between trifarotene 50 µg/g cream and vehicle cream is 6.0 (derived by supposing an increase of about 35% of the variability observed in study RD.03.SPR.105061)

GALDERMA S.A. RD.06.SPR.202395 Amended Protocol 01/Global 9Jul2021 Page 74 of 101

the sample size for a Student's t-test for paired samples can be calculated according to the following formula:

$$\geq \frac{\cdots_{n-1,1-\frac{\alpha}{2}} + t_{n-1,1-\beta}}{\left(\mu_{Trifarotene} - \mu_{Vehicle}\right)^2} \sigma_{Diff}^2$$

where $t_{\nu,p}$ is the Student's t distribution quantile with ν degrees of freedom and probability p (n is rounded up to the closest integer).

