α (2-sided)	β	Power (%)	μTrifarotene - μVehicle	σDiff		Drop-out and Non- evaluable Proportion (%)	Subjects to be Randomized
0.05	0.2	80	-1.7	6.0	100	15	118

An initial number of 118 subjects is planned to be randomised. Due to the uncertainty of the estimation of the variability, a blinded sample size re-estimation will be performed after 40 subjects complete/discontinue the study (i.e. after 33% of the initial planned subjects complete/discontinue the study) in order to evaluate the need for additional subjects to be randomized.

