### 6.1.5 Statistical Tests and Confidence Intervals

A two-sided type I error  $\alpha = 0.05$  will be used to declare statistical significance for the primary endpoints and the secondary endpoints. Confidence intervals (CIs) will be two-sided with 95% coverage for the primary endpoint and the secondary endpoints. The following flagging conventions will be applied for the p-values of all statistical testing:

- $0.01 \le \text{p-values} < 0.05 \text{ will be flagged with one asterisk (e.g. "0.0499 *")}$
- $0.001 \le \text{p-value} \le 0.01$  will be flagged with two asterisks (e.g. "0.0099 \*\*")
- $0.0001 \le \text{p-value} < 0.001 \text{ will be flagged with three asterisks (e.g. "0.0009 ***")}$
- p-value < 0.0001 will be flagged with four asterisks (e.g. "< 0.0001 \*\*\*\*")

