### **6.3.6.9** Analysis Visits Definition

Efficacy and safety by-visit summaries and analyses will use analysis visits. Both scheduled and unscheduled visits (including early termination visit) will be windowed based on the following analysis visit windows.

_	-
- (	_)
- 2	к
- (	נו
- 2	_
	>
-	5
	7
- 2	
- 5	₹
č	5
2	5
2	5
2	5
\nn	

Analysis Visit	Target Study Day	Analysis Visit Window
Baseline	1	<= 1
Week 1	8	4 - 11
Week 2	15	12 - 19
Week 4	29	22 - 36
Week 8	57	50 - 64
Week 12	85	75 - 95
Week 16	113	103 - 123
Week 20	141	131 - 151
Week 24	169	>= 159

If two or more assessments (include both scheduled and unscheduled assessments) are available for the analysis visits then all assessments will be listed and the following rules will be applied for determining the values to be used for the summaries and analyses.

- Efficacy assessments: the assessment taken closest to the target study day will be used for the summaries and analyses;
- Safety assessments, excluding clinical laboratory tests: the assessment taken closest to the target study day will be used for the summaries and analyses;
- Clinical laboratory tests: the latest assessment will be used for the summaries and analyses.

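### Ending study participation for repeated video non-compliance gives up Week 24 scar counts that the protocol elsewhere tries to collect

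*Protocol*

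**What the plan says.** **The video rule.** Site staff review at least two videos per visit interval. Under Protocol 5.4.6.5, subjects with repeated non-compliance on video, after repeated counselling and retraining, "should be discontinued from the study, based on investigator discretion". A note in the same section says it again: "Repeated noncompliance observed by video evidence should result in subject termination", also at the investigator's discretion. SAP 3.3.6 carries both statements. Both end study participation, not only study drug.

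**The retention rule.** Protocol 5.3.4 says: "Subjects who prematurely discontinue study drug will be encouraged to complete the scheduled study visits". The stated purposes are safety and obtaining at least the primary endpoint data. The same section, with 5.5.1, gives a separate rule for subjects who leave the study: they have an early termination visit with the Week 24 procedures. Table 1 lists non-compliance with study drug among the possible reasons for leaving.

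**How the exit count is used.** SAP 6.3.6.9 says: "Both scheduled and unscheduled visits (including early termination visit) will be windowed based on the following analysis visit windows". The Week 24 window starts at day 159.

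**Analysis.** The ITT population is all randomised subjects (Protocol 7.3.1, SAP 5.1). Missing scar counts are multiply imputed under missing at random by regression on earlier counts, separately by treatment (SAP 6.3.3 and 6.3.6.2). Sensitivity analyses are jump-to-reference with missing differences set to zero, LOCF, observed cases and per protocol (Protocol 7.4.3.4, SAP 6.3.4). The PP population requires 80% to 120% compliance and no major deviation that could significantly affect efficacy (Protocol 7.3.2, SAP 5.2).

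**The concern.** A subject who stops the products altogether is encouraged to stay for the Week 24 count, while one who applies them badly is to leave. The second subject's primary outcome is then usually unobserved, for a reason that arises after randomisation, depends on adherence and is judged site by site.

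The imputation model uses earlier scar counts only. It has no term for compliance, so it relies heavily on subjects who remained and who were, by selection, the better appliers. If poor or wrong-side application reduces the difference between sides, the imputed differences will tend to be too large and the ITT estimate will drift towards the per-protocol one. The exits also add to the missing Week 24 data, and the documents do not say whether the 15% allowance was meant to include them.

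**Working it through.** **1. The plan's own figure.** Inputs from Protocol 7.2: two-sided alpha 0.05, power 80%, mean paired difference -1.7, SD of the difference 6.0, 15% drop-out or non-evaluable.

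- n ≥ (t(0.975, n-1) + t(0.80, n-1))² × 6.0² / 1.7², iterated, gives n = 100. The exact noncentral-t calculation also gives 100 (power 80.1%).
- 100 / (1 - 0.15) = 117.6, rounded up to 118.

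Both stated figures reproduce.

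**2. Does the early termination count replace Week 24?** Only from day 159. The windows in SAP 6.3.6.9 also leave gaps:

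| Days in no window | Number of days |
|---|---|
| 2-3 | 2 |
| 20-21 | 2 |
| 37-49 | 13 |
| 65-74 | 10 |
| 96-102 | 7 |
| 124-130 | 7 |
| 152-158 | 7 |
| Total | 48 |

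Days 2 to 158 are 157 days, and 48/157 = 31%. An exit count on one of those days belongs to no analysis visit. On the other days before 159 it informs an earlier visit, and through that the imputation or LOCF, but it is not a Week 24 value.

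**3. Shift in the ITT mean.** Let k subjects be removed before day 159, with true mean difference d and mean imputed difference m. The mean over 118 subjects moves by (k/118) × (m - d). The documents give neither k nor d; the values below are assumptions, with m = -1.7 (the planned effect).

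| k | d = 0 | d = -0.85 |
|---|---|---|
| 6 (5%) | 6/118 × 1.7 = 0.09 | 6/118 × 0.85 = 0.04 |
| 12 (10%) | 12/118 × 1.7 = 0.17 | 12/118 × 0.85 = 0.09 |

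The shift makes the effect look larger. For scale, the planned standard error is 6.0/√118 = 0.55, so 0.09 is about 0.16 and 0.17 about 0.31 standard errors. The d = 0 column is an upper bound for these k, provided that no removed group truly favours vehicle. The imputation uses each subject's own earlier counts on each side, so if the two sides have stayed alike, m is pulled towards 0.

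**4. Power on observed Week 24 pairs, 118 randomised.** Missing rates above 15% are assumptions.

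| Missing | Pairs | Power |
|---|---|---|
| 0% | 118 | 86.3% |
| 15% | 100 | 80.1% |
| 20% | 94 | 77.6% |
| 25% | 88 | 74.8% |

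**5. The zero-difference sensitivity analysis.** With 15% missing for any reason, its expected difference is 0.85 × 1.7 = 1.45 in size, with power 79.9%. With 20% missing it is 0.80 × 1.7 = 1.36, with power 77.3%.

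**The case against.** The strongest reply is that the plan is coherent and already guards against this. Most of that reply stands, and it rules out several stronger readings.

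- **That the protocol contradicts itself.** A reader might infer this, but 5.3.4 has one rule for subjects who stop study drug, who are only encouraged to stay, and another for subjects who leave the study. Table 1 names non-compliance as a reason for leaving. The rules pull in different directions; they are not logically incompatible.
- **That one video flag removes a subject, or that removed subjects leave ITT.** Neither holds. Exit needs repeated non-compliance despite retraining, and then discretion. ITT remains all randomised subjects. What is lost is the observed Week 24 count.
- **That the analysis ignores the problem.** The jump-to-reference analysis sets missing differences to zero, which is the d = 0 assumption above. It is a sensitivity analysis, however, and it treats every missing difference alike. It can neither isolate these exits nor recover what was not measured.
- **That removal serves no purpose because the PP rule already deals with non-compliance.** The documents do not support this. The 80%-120% rule counts applications from the subject's own dosing calendar, so someone who swaps or mixes sides can record full compliance. Video checks which product went where, and 5.4.6.5 presents the video check as protecting the split-face design.
- **That the code-break rule is the same defect.** Protocol 5.4.10 says "the subject must be withdrawn from the study after completing early termination procedures" if the investigator breaks the code. An investigator who knows the allocation may also be the scar rater, so later counts could be biased. That is a real trade-off and a separate matter.

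**Conclusion.** The point holds as a gap between the video rule and the protocol's own aim of collecting the primary endpoint. A subject removed before day 159 normally has no observed Week 24 count, and the primary result then rests on a missing-at-random model that contains nothing about the adherence that caused the exit.

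The likely size is modest: at most 0.09 scars for 6 such exits and 0.17 for 12, against a planned effect of 1.7. This assumes a true difference of 0, imputation at -1.7 and no removed group that truly favours vehicle. The numbers of exits are assumed, so these figures show scale and are not a forecast.

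A reader might infer that the sample size is wrong or that the 15% allowance will be exceeded. The documents support neither: 100 and 118 reproduce, and the allowance covers drop-out and non-evaluable subjects without saying which exits were counted. The change is still worth making, because the missing data are partly avoidable and the remedy is cheap.

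**What to change.** Reconcile Protocol 5.4.6.5 and SAP 3.3.6 with Protocol 5.3.4 so that ending study drug and ending study follow-up are separate decisions.

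- Leave decisions on study drug to the existing rules; nothing here bears on them.
- Ask subjects with repeated video non-compliance to attend the remaining scheduled scar counts to Week 24, unless they withdraw consent.
- Record repeated video non-compliance as a protocol deviation, to be classified for the PP population before the blind is broken, as SAP 6.3.6.6 already provides for deviations. The calendar rule alone may miss wrong-side application.

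The cost is a clarifying sentence in each document and one deviation category. The visits are already in the schedule. Some subjects will decline to return, and the prospect of removal will motivate compliance slightly less. The code-break rule in Protocol 5.4.10 is not part of this change.

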5.4.7 Method of Subject ID and Treatment Assignment

Upon signature of the ICF, each subject will be assigned a Subject Identification Number (SIN) to be used throughout the study. Once a SIN has been assigned, that number must not be used again for any other subject. Subjects may be re-screened once provided the reason for rescreening is not related to atrophic scar counts, acne severity (IGA) or lesion counts.

Prior to the start of the clinical study, a randomization list will be generated and transmitted to the clinical packaging organization for study drug labeling. The randomization will assign the trifarotene (CD5789) cream or trifarotene vehicle cream to the right or left side of the face, for each study drug kit, and study drug instructions will include which study drug should be applied on which side of the face.

NOTE: For the purposes of this protocol, the "left" or "right" side of the face is always defined as the subject's left or right.

Upon chronological order of confirming subject eligibility, subjects are assigned a study drug kit in ascending numerical order of kit ID.

Refer to Section 5.1.1 for an illustration of the study design and split-face treatment allocation.

GALDERMA S.A. RD.06.SPR.202395 Amended Protocol 01/Global 9Jul2021 Page 48 of 101

5.4.8 Dose Modification

If a subject experiences persistent skin dryness or irritation, the Investigator may consider a reduced application frequency for the study drug in the first 4 weeks of the study, for a maximum duration of 2 weeks. In such cases, the treatment on each CCI should be reduced in a similar fashion, even if the irritation is only on one CCI

Subjects should be instructed to capture all missed applications in the dosing calendar. Sites will record the timing and details of a prescribed dose reduction for topical medication in source records.

Signs and symptoms of local cutaneous irritation will be considered as Adverse Events if they are severe enough to lead to permanent discontinuation of study drug or if they require the use of concomitant treatment including OTC products (other than moisturizers). Refer to Section 6.11.1 for further details on local tolerability assessment.

5.4.9 Allocation Concealment and Blinding

Allocation concealment is ensured as the kits will be assigned in chronological order on the basis of the confirmed subject eligibility. Randomization will occur individually, each kit will be assigned to a unique randomized subject and the simultaneous randomization of groups of subjects will be prevented.

All attempts will be made to keep the study team, site staff and subjects blinded to study treatment throughout the study, including:

- Members of the study team or site staff will not have access to the randomized treatment assignment.
- Study drug will have similar appearance, packaging and use instructions as the corresponding vehicle.

